## Protocol

86 healthy subjects took part in the study (61 females), with a mean age of 52.8 (SD=17.0, range 25-85) and a mean of 14.0 years of education (SD= 5.2, range 3-31). The distribution of demographic data is shown in Table 2. Subjects with past or present neurological or psychiatric diseases were excluded from the study, as well as subjects with visual disturbances. The presence of myopia or astigmatism did not represent an exclusion criteria if they were corrected by the use of glasses. All participants took part in the study on a voluntary basis after having provided their written informed consent and without receiving any reward. Each VST was administered twice to each participant, with an interval of two weeks, in order to analyze the test-retest effect.

The Visual Scanning Test (VST) involved a visual search for a target between similar visual distractors, projected in the far space. The VST required the presence of a blank wall and a projector and, to be carried out, participants must be positioned in a manner to reproduce a visual field of 52° x 45 °.

Overall, the VST is composed by four trials of 20 cases, each made up by 20 stimuli (see fig 1). On about the 80% of cases, the test provided the presence of target in the left, center or in right hemispace. In the remaining 20% of cases, the test provided the presence of a catch trial ("CT", absence of the target), to assess the presence of frontal disturbances or malingering. The test is constructed according to an increasing attentional load for the target on the left-hemispace.

Firstly, participants were required to look at a fixation point to always ensure the same starting position. After the start provided by the experimenter, participants were required to actively and free explore the visual field to search for the visual target. During the visual search, they were instructed to detect the presence of a target and naming its identification (saying YES or NO). Two types of errors could be made:

- Saying "NO" during the visual search in cases where the target was present;
- Saying "YES" during the visual search in the CT condition.

The experimenter recorded the reaction times (RTs) from the beginning of the visual search until participant's answer and the accuracy (HITs), through a dedicated response form. Specifically, the experimenter was required to draw a sign in case of error.

From the recorded data it may be possible to obtain several indexes, mainly related to the reaction times and to the accuracy on VST.

Indexes for *reaction times* (RTs) were related to :

- The total VST RTs (**RTs Total**)
- mean visual searching time for left hemispace (**RTs left**);
- mean visual searching time for right hemispace (**RTs right**)
- the time between the presentation of the visual field and the wrong non-identification of the target (answer "NO", where the target exists, **RT misses**);

- *Catch trials* RTs, that is the time between the presentation of the visual field and the wrong identification of the target (answer “YES”, where the target doesn’t exist, **CT- RTs**);
- The time between the presentation of the visual field and the identification of targets in the left hemisphere in Trial A (**RTs Trial A left**);
- The time between the presentation of the visual field and the identification of targets in the right hemisphere in Trial A (**RTs Trial A right**);
- The changes from mean RTs in trial A to mean RTs in trial D for left hemisphere, which reflect and implicit learning of target position to the left (i.e. Learning index, **LEI left**);
- The changes from mean RTs in trial A to mean RTs in trial D for right hemisphere, which reflect and implicit learning of target position to the right (i.e. Learning index, **LEI right**);
- Space Asymmetry index due to time (**SAI Time**), where RT total represents the RTs average value over the four trials.

Indexes for *accuracy* (HITs) were:

- The total VST HITs (**HITs Total**);
- The accuracy for left hemisphere (**HITs left**);
- The accuracy for right hemisphere (**HITs right**)
- The number of non-existing targets identified (answer “YES”, where the target doesn’t exist, **CT- HITs**);
- Space Asymmetry index due to accuracy (**SAI HITs**), where HITs total represents the accuracy average value over the four trials.

### Statistical analysis Plan

Data were analyzed using SPSS version 25 (SPSS Inc., Chicago, IL, USA). A multiple linear regression model was first applied to test the independent effects of age, sex, and education on the above mentioned indexes. The best fitting linear model for each index was sought to adjust original scores according to the demographic variables found to be associated with each index ( $p<0.05$ ). The effect of education level was explored after logarithmic, quadratic and reciprocal transformation, while age was included in the models after logarithmic transformation: “ $\log(100\text{-age})$ ”, as suggested by Capitani et al [1]. Corrected scores were calculated by adding (or subtracting) the contribution of each variable for each age group (25-45, 46-65, 66-85) and/or education level ( $\leq 5$  years, 6-13 years,  $\geq 14$  years) [2]. Based on the obtained results, correction grids were created. No adjustment was made to the top end of the scale, to avoid errors due to the fixed upper limit of the test scores. Adjusted scores were then ranked, and by means of a non-parametric procedure [3] tolerance limits (both outer and inner one-sided) were defined. Above the outer tolerance limit, it is expected to find at least 95% of the normal population (with 95% confidence), while above the inner tolerance limit, it is expected to find at most 95% of the population (with 95% confidence). The scores falling between the outer and inner tolerance limits are defined “borderline scores” because a controlled judgment cannot be expressed. Given our sample size, outer and inner tolerance limits were fixed, respectively, based on the values of the first and ninth ranked scores, after demographic adjustments. Finally, after having tested the adjusted scores for normality, differences between LEI left and LEI right, CT HITs and HITs total, and RTs trial A left and RTs trial A right, were evaluated by using a paired t-test or a Wilcoxon Signed Ranks Test, accordingly. A significant level of  $p<0.05$  was used in all tests. CT-RTs, RTs total and RT misses values were compared by using a repeated measures ANOVA followed by Bonferroni’s multiple comparison tests, if the ANOVA test showed significance ( $p<0.05$ ).

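### Age is fitted as a continuous log(100-age) but corrected by three wide bands; in the 66-85 band at least a quarter of the modelled age change stays uncorrected at one end

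*Combined protocol and SAP*

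**What the plan says.** All of this is in the Statistical analysis Plan section unless noted.

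- The model is continuous in age: "age was included in the models after logarithmic transformation", as log(100-age).
- Correction applies only where an effect is retained at p<0.05. The aim is to "adjust original scores according to the demographic variables found to be associated with each index".
- The correction is by band: "Corrected scores were calculated by adding (or subtracting) the contribution of each variable for each age group (25-45, 46-65, 66-85"). Then: "Based on the obtained results, correction grids were created".
- The adjusted scores are ranked, and "outer and inner tolerance limits were fixed, respectively, based on the values of the first and ninth ranked scores".
- For the zone between the limits ("The scores falling between the outer and inner tolerance limits are defined" borderline), the plan says that no controlled judgment is possible.
- One exception is made at the ceiling: "No adjustment was made to the top end of the scale, to avoid errors due to the fixed upper limit of the test scores".
- The Protocol section describes 86 healthy subjects with a "mean age of 52.8 (SD=17.0, range 25-85".

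The plan does not give the age within each band at which the contribution is evaluated. It mentions neither a correction at individual age nor a check for age trend left in the adjusted scores.

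**The concern.** The function log(100-age) changes slowly in young adults and fastest at the oldest ages. A single constant over 66-85 is therefore coarsest, in modelled terms, where the chosen curve is steepest. Within that band the younger people are over-corrected and the older ones under-corrected, and the correction jumps at the 65/66 boundary although the model barely moves there.

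At stake is comparability across ages, which is the purpose of an age correction. If the limits are set on band-corrected scores, healthy people in their early eighties will be called borderline or abnormal more often than intended. People in their late sixties will be held to a more lenient standard. Two healthy people aged 65 and 66 with almost the same modelled score can be classified differently.

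**Working it through.** **The plan's own figure.** The ranks depend only on n=86 and 95% content. With X binomial(86, 0.05), P(X≥1)=0.988 and P(X≥2)=0.933, so the outer limit is rank 1. P(X≤7)=0.934 and P(X≤8)=0.972, so the inner limit is rank 9. Both stated ranks are right.

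**Share of the modelled change in each band.** The inputs are the transform, the bands and the 25-85 range, all from the documents. The coefficient and the log base cancel. The total is ln(75/15)=1.609.

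| Ages | Change | Share |
|---|---|---|
| 25-45 | ln(75/55)=0.310 | 19.3% |
| 46-65 | ln(54/35)=0.434 | 26.9% |
| 66-85 | ln(34/15)=0.818 | 50.8% |

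The remaining 2.9% lies in the one-year steps 45-46 and 65-66.

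**Smallest possible remainder.** With one constant evaluated inside the band, the remainders at 66 and 85 add up to 50.8%. The larger is at least 50.8%/2=25.4%.

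**Remainder for plausible constants.** At age 85 it is ln((100-ref)/15)/1.609. At age 66 it is 50.8% minus that.

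| Constant used for 66-85 | At 66 | At 85 |
|---|---|---|
| Reference age 73.3 | 15.0% | 35.8% |
| Midpoint 75.5 | 20.4% | 30.5% |
| Reference age 77.6 | 25.9% | 24.9% |
| Band mean, uniform ages | 22.2% | 28.7% |
| Band mean, ages matched to mean 52.8, SD 17.0 | 20.7% | 30.2% |

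With uniform ages the band means of log(100-age) are 4.170, 3.787 and 3.169, and about 14% of the age variance is left after correction.

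**Jump at 65/66.** The model moves by ln(35/34)=0.029. The correction moves by 0.617 (uniform ages) or 0.599 (matched ages), about 21 times as much.

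**Misclassification rates (assumed effect size).** The documents give no age coefficient. The assumptions are age R²=0.2 (range 0.1-0.4), normal residuals with SD 1, uniform ages 25-85, band-mean correction, and ranks counted from the worse end. The slope is √[R²/((1-R²)·Var(log(100-age)))]. Each cut-off is solved so that the mean tail over all ages equals 1/87=1.1% (outer) or 9/87=10.3% (inner); the difference, 9.2%, is borderline. Tails are then evaluated by age.

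| Healthy people aged | Beyond outer | Beyond inner |
|---|---|---|
| Expected at any age | 1.1% | 10.3% |
| 66-70 | 0.4% (0.6-0.2) | 5.3% (6.8-3.2) |
| 81-85 | 2.7% (2.1-4.1) | 18.4% (15.5-24.5) |
| 66-85 as a whole | 1.3% | 10.8% |

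Brackets run from R²=0.1 to 0.4. At 81-85 the excess beyond the inner limit is 18.4-10.3=8.1 points. Of these, 15.7-9.2=6.5 are borderline and 2.7-1.1=1.6 lie beyond the outer limit. At age 65 against 66, 15.3% and 4.6% fall beyond the inner limit. Reference ages from 77.6 to 73.3 give 2.4-3.2% and about 17-21% at 81-85.

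**With the slope estimated.** In a simulation of 12,000 samples of 86 with matched ages, kept if age reached p<0.05 (11,917 kept at R²=0.2), mean rates beyond outer/inner were:

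| Ages | Bands | Exact age |
|---|---|---|
| 81-85 | 3.2% / 20.1% | 1.4% / 11.1% |
| 66-70 | 0.5% / 5.8% | 1.2% / 10.6% |

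The band figures differ slightly from the table before because the age distribution differs. Over all ages, achieved confidence was about 98% for both limits under either method, so the stated 95% is met.

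**The case against.** **The wording does not settle one constant per band.** The scores that were ranked could have been corrected at exact age, with bands used only for the published grid. This stands as an uncertainty: the rates above, which band both scores and limits, would then not apply as given. The remainder would still reach every grid user, whose banded score would be compared with limits built from exact-age scores.

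**The 50.8% depends on a curve that is prescribed, not shown to fit.** If the true effect is linear, 66-85 holds 19/60=31.7% of it and the floor falls to 15.8%. At R²=0.2 with uniform ages, exact-age log correction would then over-correct 81-85, giving 0.7% and 7.4% beyond outer and inner, against 1.7% and 13.9% with bands. Exact age is still nearer to 1.1% and 10.3%, but not by much. At 66-70 its advantage is clear: 1.4% and 12.0%, against 0.6% and 6.5%. A check of the curve is therefore needed as well.

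**The size is assumed.** No coefficient is reported, and some indexes may keep no age term. With n=86 a single age term reaches p<0.05 at R² of about 0.045. At R²=0.05 the rates at 81-85 are 1.8% and 13.8%, so the lower ends quoted above are too high for weak retained effects. This reduces the harm but does not remove it.

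**The harm is bounded.** Most of the excess is borderline, the 66-85 band as a whole is close to target, and banding is far better than no correction (5.8% and 33.5% at 81-85 for R²=0.2). All of this is correct. It argues for a modest priority, not for leaving the mismatch.

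**Conclusion.** The concern holds. The 50.8% share and the 25.4% floor follow from the plan's own transform, bands and age range, on the natural reading of one constant per band. They are shares of the modelled 25-85 change and need no effect size. The classification rates do need one, and are illustrative.

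The plan's whole-population 95%/95% claim is not breached; the fault is that errors are redistributed by age. It concerns only indexes with a retained age effect that worsens with age. The rates ignore the no-adjustment rule at the ceiling, so they fit reaction-time indexes better than accuracy indexes. This is a worthwhile and inexpensive improvement, held with medium confidence because the coefficients and reference ages are not given.

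**What to change.** - Compute each age-adjusted score at the participant's exact age: score minus b × [log(100-age) minus the sample mean of log(100-age)]. Rank these scores for the tolerance limits, and publish the equation as the primary correction.
- Keep any grid as a convenience table, with narrower bands from age 66 (for example five years) and stated reference ages. Band-mean correction in five-year bands leaves at most 4.0% (66-70), 4.8% (71-75), 5.9% (76-80) and 7.7% (81-85) of the modelled change, against 29-30% now. In the simulation, exact-age limits used with such a grid gave 1.4% and 11.2% at 81-85.
- For each corrected index, report a comparison of log(100-age) with linear age, and the age slope left in the adjusted score.
- If ranking was already done at exact age, say so.

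**Cost.** No new data: the fitted equations and ages exist. Users need a formula or a longer grid, and a finer grid still has small steps. The correction relies more on the fitted curve where participants are few, about 5 of 86 at 81-85 if ages match the stated mean and SD (an assumption). Within 81-85, where the plan promises no confidence level, the simulation at R²=0.2 puts outer-limit confidence at 96% rather than 80%, but inner-limit confidence at 89% rather than 99.9%, because slope error is largest there.

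### The single lower-tail cut-off rule, as written, points the wrong way for the five search-time indexes, and for CT-HITs it depends on a definition the plan must reconcile

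*Combined protocol and SAP*

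**What the plan says.** The Statistical analysis Plan section describes one procedure: regress the listed indexes on age, sex and education, adjust, rank, and read off two one-sided non-parametric limits. The outer limit is described by "Above the outer tolerance limit, it is expected to find at least 95% of the normal population (with 95% confidence"; the inner limit is the value above which at most 95% should lie, also with 95% confidence. The ranks are then fixed: "outer and inner tolerance limits were fixed, respectively, based on the values of the first and ninth ranked scores, after demographic adjustments". Nothing says whether ranking runs from low to high or from worst to best, and no index is treated differently.

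Two nearby sentences might seem to settle the direction:

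- "Corrected scores were calculated by adding (or subtracting) the contribution of each variable for each age group" concerns the sign of the demographic contribution.
- "No adjustment was made to the top end of the scale, to avoid errors due to the fixed upper limit of the test scores" presupposes a scale with a ceiling.

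The Protocol section lists both accuracy scores and elapsed times. The plain search times are RTs Total, RTs left ("mean visual searching time for left hemispace"), RTs right, RTs Trial A left ("The time between the presentation of the visual field and the identification of targets in the left hemisphere in Trial A") and RTs Trial A right. CT-HITs stands under accuracy but is defined as "The number of non-existing targets identified".

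**The concern.** A limit defined by the share of normals above it is a lower-tail limit, which is right only where low scores are bad. An RT runs from the start of the search until the answer, so a larger value is a slower search and, on the natural reading of a search test, a worse one. The abnormal tail for the five search times is therefore the upper one.

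The cut-offs are the product of this normative study. If the rule was applied literally to times, slow searchers land on the normal side, while the fastest healthy searchers are called abnormal or borderline. If times were ranked from slowest, the cut-offs are sound but their printed definition is wrong. A user of the norms cannot tell which case applies.

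CT-HITs raises the same question in a different form. By its definition it counts false YES answers, which the Protocol section lists as an error, so a high value is bad. Its name, its place under accuracy and its paired comparison in "differences between LEI left and LEI right, CT HITs and HITs total, and RTs trial A left and RTs trial A right" suggest correct rejections, for which a low value is bad.

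**Working it through.** **Inputs.** From the documents: n = 86 healthy subjects (Protocol section); 95% coverage, 95% confidence, one-sided, ranks 1 and 9 (Statistical analysis Plan section). Assumed, because the documents give no RT distribution and no patient data: normally distributed scores, equal SD, and slowing of 1, 2 or 3 SD.

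**1. The plan's ranks reproduce.** Let B be binomial with n = 86 and p = 0.05.

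- Outer limit: the largest r with P(B ≥ r) ≥ 0.95. Rank 1 gives 1 − 0.95^86 = 98.8%; rank 2 gives 93.3%. So r = 1.
- Inner limit: the smallest r with P(B ≤ r − 1) ≥ 0.95. Rank 8 gives 93.4%; rank 9 gives 97.2%. So r = 9.

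The rank numbers are right for one tail. Only the choice of tail is in question.

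**2. Neither ranking order rescues the wording for a time.** The expected share of normals beyond the r-th score from either end is r/(n + 1), for a random sample from a continuous distribution.

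- *Ascending.* Both statements about the share above are true, but the limits are the fastest and ninth-fastest healthy times. On average 1/87 = 1.1% of healthy people fall below the outer limit and 9/87 = 10.3% below the inner, and these are the fastest searchers.
- *From slowest.* The limits sit in the right tail, but on average only 1.1% of normals lie above the outer limit and 10.3% above the inner. The statement that at least 95% lie above the outer limit would hold with probability 0.05^86, about 1e-112. The inner statement (at most 95%) is true but says nothing useful.

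**3. Mirrored ranks for the upper tail.** n + 1 − r gives 86 + 1 − 1 = 86 (outer) and 86 + 1 − 9 = 78 (inner). The confidence is unchanged at 98.8% and 97.2%.

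**4. Consequence if the ascending reading was used.** For a person with score x from N(d, 1), the chance of lying beyond a limit is the average over x of P(Bin(86, F(x)) ≤ r − 1) for the lower tail, or of P(Bin(86, 1 − F(x)) ≤ r − 1) for the upper tail. F is the standard normal distribution function and r is 1 or 9.

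| Slowing d | Lower tail, outer / inner | Upper tail, outer / inner |
|---|---|---|
| 1 SD | 0.07% / 1.2% | 9.0% / 39.0% |
| 2 SD | 0.002% / 0.06% | 34% / 76% |
| 3 SD | below 0.0001% / 0.001% | 69% / 95% |

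**5. CT-HITs, if it counts false alarms.** Once 9 of the 86 healthy subjects have no false alarm, the first and ninth ascending scores are both 0 before adjustment, and no raw count can fall below them.

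**6. Indexes with fewer values.** As defined, RT misses and CT-RTs exist only for subjects who made the error in question. Repeating step 1 for smaller n gives outer/inner ranks 1/9 for n = 82 to 92, 1/8 for 68 to 81 and 1/7 for 59 to 67. Below 59 no outer 95%/95% limit exists.

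**The case against.** The strongest reply is that the authors may well have ranked times from worst to best. The cut-offs would then be correct, and the fault would be an unstated ranking order and one ill-suited word. That is possible and cannot be excluded from the text. It limits the claim to the rule as written and makes the figures in step 4 conditional. It does not remove the defect, because the printed outer statement is then false for times.

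A variant reads *above* as the better-performing side, which would make slowest-first ranking consistent with the sentence. This is strained: the section speaks of ranked scores and never defines the word that way.

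Other points stand in part:

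- Slower being worse is inferred from the nature of the task; the documents do not say it. Calling scores beyond the outer limit abnormal is also inferred, since the plan names only the borderline zone.
- The probability in step 2 for slowest-first ranking measures a faulty sentence, not any misclassification.
- The zero limit for CT-HITs is shown only before demographic adjustment, which could move scores off zero.
- The reduced n for CT-RTs follows its Protocol definition. The planned repeated measures ANOVA with RTs total and RT misses needs values on all three, so that definition also deserves confirmation.

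No limits may have been intended for times at all. The section does not say so, and it should if that is the case.

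**Conclusion.** The concern holds and needs correction before the cut-offs are used. The rule fits HITs Total, left and right. For the five search times it is wrong as written: depending on the unstated ranking order, either the cut-offs or their definition must be wrong. In the first case, someone 2 SD slower would lie beyond the limits with probability 0.002% (outer) or 0.06% (inner), against 34% and 76% in the correct tail, given normal scores and equal SD. In the second case nobody is misclassified. CT-HITs is unresolved, because its definition and its use point to opposite tails. SAI and LEI cannot be judged from the text and are not counted as errors. The argument about direction needs only that slower is worse; the rank results need no distributional shape beyond continuity.

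**What to change.** State the abnormal tail and the ranking order for each index.

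- **HITs Total, left, right:** keep ascending ranks 1 and 9.
- **Five search times:** use upper limits at ascending ranks 86 (outer) and 78 (inner). Reword so that at least 95% of normals lie below the outer limit and at most 95% below the inner, each with 95% confidence. Check any published time cut-offs against this. If no limits were set for times, say so.
- **CT-HITs:** reconcile the definition with its use as an accuracy score. Then take the upper tail if it counts false alarms, or the lower tail if it counts correct rejections.
- **RT misses and CT-RTs:** state the tail, and take the ranks from the number of subjects with a value, counted from the abnormal end, as in step 6.
- **SAI and LEI:** derive the tail from their formulas and state it.

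The cost is a few sentences in the SAP and re-reading ranks from data already sorted; no new data are needed. The one possible loss is the outer limit for RT misses or CT-RTs, which must be withheld if fewer than 59 subjects have a value.

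### The paired comparisons appear to use scores adjusted by a separate model for each index, so unequal corrections can alter the difference being tested

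*Combined protocol and SAP*

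**What the plan says.** All of this is in the Statistical analysis Plan section of the combined document.

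- Modelling is done index by index: "The best fitting linear model for each index was sought to adjust original scores". Only variables with p<0.05 for that index are carried into its correction.
- The functional form can also differ between indexes: "The effect of education level was explored after logarithmic, quadratic and reciprocal transformation".
- Corrections are constants for three age bands and three education bands. The group or value at which the correction is zero is not given.
- There is an exception for bounded scores: "No adjustment was made to the top end of the scale". The stated reason is the fixed maximum of the test scores.
- The sentence that opens "Finally, after having tested the adjusted scores for normality" then compares LEI left with right, CT HITs with HITs total, and RTs Trial A left with right. A paired t-test or a Wilcoxon signed-rank test is chosen from the normality result.
- For the repeated-measures ANOVA of CT-RTs, RTs total and RT misses, the plan does not say whether raw or adjusted scores enter.

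That the paired tests use adjusted scores is an inference, though a strong one. Checking adjusted scores for normality in order to pick the test makes sense only if those scores are then tested, and no raw-score comparison is described.

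**The concern.** Demographic correction serves comparisons between people, such as placing one patient against a normative limit. In a paired comparison each person is their own control, so age, sex and education cannot confound the left-right contrast.

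The correction can still do harm. Left and right are modelled separately, so they may receive different constants, or only one side may pass p<0.05 and be corrected. Any inequality in the average correction enters the mean difference under test. Even when the averages are equal, removing demographic variation from the scores can make the standard error too small. What is at stake is whether a reported asymmetry in learning or search time, or its absence, describes the subjects or partly reflects the correction.

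**Working it through.** **The plan's own figure.** The one design figure that can be recomputed is the pair of tolerance-limit ranks at n=86. With X ~ Binomial(86, 0.05):

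- Outer limit: P(X≥1) = 1 − 0.95^86 = 0.988 and P(X≥2) = 0.933, so rank 1.
- Inner limit: P(X≤7) = 0.934 and P(X≤8) = 0.972, so rank 9.

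Both stated ranks reproduce. The present point does not touch them.

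**Inputs.** From the Protocol section: n=86, and subjects "with a mean age of 52.8 (SD=17.0, range 25-85" years. Not given, and therefore assumed: the left-right residual correlation (0.5 to 0.8), the standardised age slopes (0 to 0.6) and the reference point of the correction. Tests are taken as two-sided at 0.05.

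**Effect on the mean.** Write the adjusted scores as L − c_L and R − c_R. The adjusted difference is (L − R) − (c_L − c_R), so its mean moves by −(mean c_L − mean c_R). That is zero if both corrections average zero over the sample. Otherwise it is generally not zero.

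**Effect on the standard error.** Take unit-variance scores, age slopes −0.4 (left) and 0 (right), residual correlation 0.8 and exact centring.

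- Raw variance of the difference: 2 − 2 × 0.8 × √(1 − 0.16) = 0.534.
- After correction: 0.534 − 0.4² = 0.374.
- Ratio of standard errors: √(0.374/0.534) = 0.84.
- The mean difference has not changed, so the effective critical value is 1.96 × 0.84 = 1.64, a two-sided error of about 10%.

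Simulation of this case gave 11.5%, against 6.5% on raw scores in the same run.

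**Null simulations.** Equal left and right population means, n=86, paired t-test, correction only for terms with p<0.05. One set used residual correlation 0.7 with ages uniform on 25–85 (mean 55, SD 60/√12 = 17.3). The other used correlations 0.5 and 0.8, a choice among education transformations, and 800 replicates per setting. Its simulated age SD was about 14.6, against 17.0 in the document.

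| Scores tested | Equal slopes, corr. 0.7 | Equal slopes, corr. 0.5 and 0.8 | Unequal slopes, corr. 0.7 | Unequal slopes, corr. 0.5 and 0.8 |
|---|---|---|---|---|
| Raw | 4–5% | 5.0–5.5% | 4–5% | 4.8–6.5% |
| Adjusted, exactly centred on sample mean | 4–5% | 4.9–5.8% | up to 8% | 6.5–11.5% |
| Adjusted, banded, central reference | 5–8% | 5.2–6.8% | 7–31% | 8.1–12.4% |
| Adjusted, banded, referenced to one group (youngest band at corr. 0.7) | 10–28% | 27.1–34.9% | over 70% | 83.4–96.6% |

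With 800 replicates the Monte Carlo standard error at 5% is √(0.05 × 0.95/800) = 0.8 percentage points, so the raw-score results agree with 5%.

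With identical true slopes, the two indexes still ended with different covariate sets in 16–43% of replicates. A further age-only run (correlation 0.7, slopes 0.15–0.30 SD, 3000 samples per setting) corrected one side alone in 18–25% of samples. It gave about 5–6% error with a central reference and 26–32% with the youngest band as reference.

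**Top-end rule.** For scores with a ceiling (correlation 0.5, centred correction, top scores left unadjusted), error was 4.4–4.8% with equal slopes. With unequal slopes it was 7.9–11.1%, with a mean shift of about 0.03–0.05 SD. Raw scores gave 4.0–5.1%.

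**The case against.** The best defence is that the harm may be negligible. If the constants are centred on the sample and demographic effects are equal on both sides, error stays near 5%. Adding or subtracting contributions is compatible with correction around a centre, and the method is taken from a cited source that cannot be consulted here. This stands as far as it goes: the documents do not show that the tests are badly inflated. But they do not state the centring either, and centring protects only the mean, not the standard error. Equal slopes are not assured: the Protocol section says attentional load was built to increase for targets on the left.

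Four stronger readings are tempting and are not supported.

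- *That error is 25–35%.* This needs a grid referenced to one extreme group and slopes near the p<0.05 threshold. With the youngest band as reference, error was 10% at zero slope and 16–18% at slopes of 0.5–0.6. The figures above 70% also need unequal slopes; there the adjusted test in effect asks about asymmetry in the reference group, which is a different question.
- *That banding necessarily destroys centring.* If each band constant is that band's mean contribution relative to the sample mean, the average correction is exactly zero. With other sample-mean-referenced constants the shift was 0.006–0.020 SD.
- *That the top-end rule distorts the left-right tests.* It is tied to a fixed upper score limit. LEI and Trial A RTs are reaction-time indexes with no stated maximum, so the rule plausibly concerns accuracy scores only.
- *That the three-way ANOVA is known to use adjusted scores.* The plan does not say so.

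**Conclusion.** The concern holds in limited form. As written, the plan appears to test adjusted scores in three paired comparisons that need no demographic adjustment. Nothing in it ensures that both members of a pair are corrected equally. With equal true slopes, error ranges from about 5% (exact centring) through 5–8% (central grid) to a conditional worst case of about 25–35% (one extreme reference group). It is higher when slopes differ between sides.

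These figures rest on assumed slopes, correlations and reference points, and on the reading that adjusted scores enter the tests. They apply to the left-right pairs. CT HITs vs HITs total was not simulated: the Protocol section defines one as false identifications and the other as total accuracy, so equal means is not a natural null. The argument that no correction is needed covers that pair too, but the percentages do not. The point is worth correcting because the remedy is simple, and it leaves the normative output intact.

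**What to change.** - Run LEI left vs right, RTs Trial A left vs right, and CT HITs vs HITs total on raw scores.
- Choose the paired t-test or Wilcoxon test from the distribution of the raw paired differences.
- Keep adjusted scores for the correction grids and tolerance limits, and state the reference point of the correction.
- For the CT-RTs, RTs total and RT misses ANOVA, state that raw scores are used.

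If an adjusted comparison is also wanted, report it as secondary, with one covariate set and a sample-mean-centred correction for both members of the pair. This protects the mean difference but not necessarily its standard error.

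The cost is a short change of wording, and repeating the normality check and the tests on data already held. If the conclusions agree with those from adjusted scores, they are firmer; if they differ, that should be reported.
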